Study Protocol

IRB ID: 20180597 (CR00012479)

Study Number: 1 R34 DA043784-01A1

Date: July 19, 2018

Study Title

Culturally Modified Family Based Therapy for Haitian Youth in South Florida
(CIFFTA).

NCT number: 03876171

Date: July 19, 2018

INSTRUCTIONS:

1) Protocol Title

Culturally Modified Family Based Therapy for Haitian Youth in South Florida (CIFFTA).

2) IRB Review History*

None

3) Objectives*

The study will pursue the following Specific Aims:

Aim 1. To adapt CIFFTA and the assessment instruments necessary to test its efficacy to the unique Haitian sociocultural contexts. This process of adaptation has the purpose of optimizing CIFFTA's acceptability and cultural appropriateness. It will rely on ethnographic methods (participant observations, focus groups, and interviews) to guide the adaptation process.

Aim 2. Determine, via a pilot efficacy trial, the impact of CIFFTA compared with standard-of-care for reduction of drug use, risky sexual behaviors, and delinquency risk among Haitian adolescents ages 13 to 17 in Miami-Dade County. The ethnographic component of the study will monitor the delivery of the intervention, collecting process data, and affording the investigators needed perspective on the intervention's impact.

Aim 3. To generate preliminary data on the usefulness of assessment tools and CIFFTA's efficacy among the population. These data will help evaluate the effect of the intervention and its best form of implementation. They will also provide preliminary evidence to justify a full clinical trial of CIFFTA in a population of at-risk Haitian youth.

Primary study outcomes include: intervention attendance and completion; sustained abstinence in substance use through biochemical verification and self-report; family functioning; sexual risk behavior; and conduct disorder. Secondary outcomes include: recidivism in delinquency, improvement in family communication, and peer/gang involvement. Outcomes will be assessed through follow-up instruments at three points: 3, 6 and 12 months.

4) Background*

Despite preventive efforts made over the last three decades, it is clear that some populations have not benefited from attempts to deter them from risky behaviors. Haitian youth constitute an important but understudied population who may be particularly

Study Protocol

IRB ID: 20180597 (CR00012479)

Study Number: 1 R34 DA043784-01A1

Date: July 19, 2018

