This is a multi-wave study, with approximately all the participants recruited by the end of Year 02 and the remainder in the beginning of Year 03. At baseline, we will conduct comprehensive assessments of all study constructs and repeat all other assessments annually. Activities during the first three months will consist of the following: Staffing, Instrument Calibration, Ethnographic Update. Each wave will be composed of 22 participants to be randomized into two groups (11 each). Each undergo assessment at intake (T1) and outtake (T2), a booster session 3 months after outtake and a final assessment at 12 months. Data analysis process will be initiated at the third month and continue throughout the study implementation.

Study Protocol

[figure not shown]
IRB ID: 20180597 (CR00012479)

Study Number: 1 R34 DA043784-01A1

Date: July 19, 2018

Publications are expected to start from month 20. The table below details the activity processes.

Project Timeline

9) Study Endpoints*

Primary outcomes are: intervention attendance and completion; sustained abstinence in substance use through biochemical verification and self-report; family functioning; sexual risk behavior; and conduct disorder.

Secondary outcomes include recidivism in delinquency, improvement in family communication, and peer/gang involvement.

10) Procedures Involved*

RCT procedures

CIFFTA has three major components – Family-Based Therapy, Individual Therapy, and Psycho-educational Modules – delivered over 16 weeks in a six sessions (60 minutes each) per month format. In this study, the therapy will be delivered in the home to reduce missed sessions and premature termination. Special training will focus on how to structure the home environment to reduce distractions. Three sessions per month will typically be a session which may include Family-based Therapy or Psycho-educational modules with the family or parents alone (e.g., parent training). The other three sessions are typically with the adolescent alone and include Motivational Interviewing or Psycho-educational modules designed for the adolescent.

Study Protocol

IRB ID: 20180597 (CR00012479)

Study Number: 1 R34 DA043784-01A1

Date: July 19, 2018

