In the early stages of treatment with the family (weeks 1-3) the therapist uses motivational interviewing to enhance the family's motivation to change their behaviors and specialized engagement strategies to make sure all family members are active in treatment of the adolescent. The therapist helps families understand the urgency of changing key behaviors but also instills hope that change is possible. The therapist helps identify the many stressors impinging on the adolescent and family.

In the early stages of treatment with the adolescent (weeks 1-3) the therapist uses motivational interviewing to develop discrepancies between current behaviors and desired outcomes and to acknowledge the stressors she/he confronts each day.

In the middle stages of treatment (weeks 4-13) family sessions focus on teaching parenting practices, increasing family cohesion and support, and reducing parenting disengagement or conflict. Psycho-educational modules are used to teach concepts (e.g., parenting, immigration and acculturation related stressors) that increase readiness for successful family therapy to improve the family's supportive interactions. Parents are helped to understand the adolescents' co-occurring disorders and vulnerabilities that underlie the behavior problems and they learn to validate the adolescent's struggles.

In the middle stages of treatment (weeks 4-13) adolescent sessions focus on setting goals for their lives, becoming more active in changing behaviors that are risky, and learning life skills that can be helpful in their day-to-day lives. Psycho-educational modules are used to teach concepts (e.g., risky drug use and sexual behavior, interpersonal effectiveness, emotion regulation) that can be generalized to everyday life.

In the later stages of treatment (weeks 14-16), both individual and family sessions focus on relapse prevention and successful termination from treatment.

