Focus Group. Focus groups will be guided by the following criteria: (a) they will be homogeneous with regard to age (parents or adolescents only); (b) they will follow a relatively structured interview guide with high involvement of the ethnographer as moderator; and (c) they will have six to ten participants each. Topical areas for the focus group will include the following: impact of the interventions; behavior changes of adolescents of parents; changes in the family.

Instrumentation.

The primary constructs for the youth participants will include: risk for re-offending, criminal history, patterns of drug/alcohol use, psychological adjustment, evidence of conduct disorder, family functioning, and acculturation. Constructs for the caregiver(s) will include their assessment of their child's conduct, family functioning, and their own level of acculturation. At baseline, information will also be gathered on participants demographic status. The instrument will be administered at participants' homes. Along with the demographic data, the baseline questionnaire will incorporate measures from the instruments described below, culminating in a unified tool taking no more than one hour to administer.

Behavioral, emotional, and academic functioning. We will administer standardized measures of youths' emotional and behavior disorders. Parent and youth reports on the Achenbach System of Empirically Based Assessment will assess youth's behavioral, emotional, and academic functioning. Parents will complete the Child Behavior Checklist (Achenbach 1983); and youth also will complete the parallel Youth Report Form (YRF). These measures yield scores for internalizing and externalizing problems and academic competence, and have DSM-5 scales for multiple problem areas: depression, anxiety, somatic, attention deficit/hyperactivity, oppositional, and conduct problems.

Risk for re-offending. Level of risk will be assessed with the Youth Level of Service/Case Management Inventory (YLS/CMI) developed by Hoge and Andrews (51) that screens for risk in eight domains (conduct disorder,

Study Protocol

IRB ID: 20180597 (CR00012479)

Study Number: 1 R34 DA043784-01A1

Date: July 19, 2018

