school, criminal friends, alcohol/drug use, leisure/recreation, personality/behavior, family circumstances, and attitudes/orientation) yielding overall risk scores ranging from (0-8). The YLS/CMI is administered to all juveniles processed in the JSD. The same instruments will be used to assess youth from the GRP.

Drug use and psychological adjustment will be assessed with the Comprehensive Adolescent Severity Inventory developed by Myers and colleagues (52). The CASI covers a broad range of psychosocial and risk behaviors including information on substance abuse (e.g. age of first use, current patterns of use, friends' use), criminal activity, mental health, peer relationships, family/household relationships, education, and sexual behavior. Among other things, the instrument gathers information concerning youth use of a range of substances and will be adapted to assess ATOD use at baseline and post-intervention. In this way, we will be able to determine participants' historical and recent use (i.e. past 30 days, past 3, 6, and 12 months), if any, of drugs and alcohol. Similar assessments are made of sexual risk behavior and a global assessment of psychological adjustment is included that yields a continuous measure of global functioning. Adequate levels of internal consistency, test-retest reliability and validity coefficients are reported.

Conduct Disorder. Youth problem behaviors will be measured using the Conduct Disorder instrument from a Revised Behavior Problem Checklist (53) utilized previously by BSFT staff (54). The RBPC is an empirically derived measure consisting of 89 problem behaviors. We will adapt the instrument to include behaviors that are particularly salient among Haitian youths and exclude others that are deemed less salient. For each youth, the primary caregivers will rate the severity of each behavior on a 3 point scale (0 = no problem, 1 = mild problem, 2 = severe problem). The Conduct Disorder Subscale as used for this study consists of 22 items ($\alpha = .92$) measuring the youth's disruptive behavior at home (e.g., "disobedient; difficult to control"). The Conduct Disorder Subscale will be administered at intake and again at termination.

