Youth Urine Toxicology. As part of our research component, we plan to collect voluntary urine specimens for analysis at the times of the youths' initial and follow- up interviews in order to validate self-report. We will follow procedures informed by NIDA's CJDATS workgroup guidelines. Urine specimens will not be collected on youths incarcerated for more than two days. The use of four substances will be probed using the Onsite CupKit® urine screen procedure (positive threshold levels are noted in parentheses): (1) methamphetamines (500 nanograms per milliliter [ng/ml] of urine), (2) opiates (300 ng/ml of urine), (3) cocaine (300ng/ml of urine), and (4) marijuana (THC) (50 ng/ml of urine). The surveillance window for the four drugs is as follows: methamphetamines and opiates = 48 hours; cocaine = 72 hours; marijuana: moderate users = 5 days; heavy users = 10 days; chronic users = 20 days. Although we considered hair analysis, urine screens were selected because of they are the most widely used and accepted method for supervision monitoring (Lipsey & Wilson, 1998), they are minimally invasive, can be collected in the community during follow-up assessments and carry fewer taboos on collection (Meyers et al., 2002). Urine screen results will be kept confidential, and will be collected in containers marked with pre-printed labels without personal identifying information. To assure integrity of the sample, the Onsite CupKit® automatically checks for temperature, and the interviewer will ensure that there is no one else in the restroom.

Overview of Assessment Procedures and Attrition

The 3-month follow-up assessment will be measured from the end of the intervention, as will be the 6-month and the 12-month follow-up

Study Protocol

IRB ID: 20180597 (CR00012479)

Study Number: 1 R34 DA043784-01A1

Date: July 19, 2018

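### The caregiver Conduct Disorder subscale is scheduled at two occasions, which conflicts with the 3-, 6- and 12-month follow-up stated for the trial's outcomes

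*Protocol*

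**What the plan says.** Protocol sections 3 and 9 list conduct disorder among the primary outcomes but name no instrument for it. The instrument described under the Conduct Disorder heading in section 10 (Instrumentation) is a 22-item caregiver-rated subscale of a behaviour checklist, each item scored 0 to 2. Its schedule is one sentence: "The Conduct Disorder Subscale will be administered at intake and again at termination".

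The other statements on timing are these:

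- Section 3: "Outcomes will be assessed through follow-up instruments at three points: 3, 6 and 12 months".
- Section 10, Overview of Assessment Procedures and Attrition, sets the clock: "The 3-month follow-up assessment will be measured from the end of the intervention". The 6- and 12-month interviews follow the same rule.
- Section 8: "Each undergo assessment at intake (T1) and outtake (T2), a booster session 3 months after outtake and a final assessment at 12 months". The same section also says that the team will "repeat all other assessments annually".
- Section 10, Study Process, says that all constructs are assessed at baseline and that assessments are repeated, and refers to the timeline for when.

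The SAP (Analytic Methods) plans latent growth models and bases their identification on the data having more than two occasions.

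**The concern.** The general schedule and the schedule for this instrument cannot both be followed as written. Field staff would normally work from the instrument-specific sentence, and ratings not taken at a follow-up interview cannot be recovered later.

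If that sentence is followed, a caregiver measure of a primary outcome gives no effect estimate at 3 or 6 months. If termination is the end of treatment, it also cannot show whether a gain lasts. That matters for a pilot whose stated use is to supply effect sizes, for rate of change and for differences at single times, for a possible full trial.

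Termination is not defined for this scale. Section 10 plans to track families that leave treatment early, but the documents do not say when outtake falls for them. They also give no length for standard of care, so an end-of-treatment rating has no fixed date in that arm.

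**Working it through.** The plan gives no figure to reproduce here. The check is a count of occasions plus an identification count.

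**1. Follow-up points covered.** The required set is 3, 6 and 12 months (section 3), counted from the end of the intervention (section 10, Overview).

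- Termination = end of treatment: this is month 0 on that clock. Covered: 0 of 3.
- Termination = 12-month final visit: covered 1 of 3; 3 and 6 months are missed.

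Either way the scale has two occasions in total.

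**2. Which reading is likelier.** For participants, section 10 (RCT procedures) uses the word for treatment: sessions in weeks 14-16 "focus on relapse prevention and successful termination from treatment". The same section uses it for families who stop therapy too soon. Intake and termination also match the T1 and T2 of section 8, where the 12-month assessment is listed separately. Section 13 uses the word for the study, but there it means stopping the trial early after data review, not a participant's visit. The end-of-treatment reading is therefore the likelier one.

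**3. Share of the observation period on that reading.** CIFFTA lasts 16 weeks (section 10). With 12 months (52 weeks) counted from its end, the period is 16 + 52 = 68 weeks, and 16/68 = 24%. Section 8 gives no origin for its 12-month assessment. If it were counted from intake, the share would be 16/52 = 31%. Both figures apply to the CIFFTA arm only.

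**4. Identification of a linear growth model** (continuous outcome, random intercept and slope, per group). With T occasions:

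- Observed moments: T means + T(T+1)/2 variances and covariances.
- Parameters: 2 growth means + 2 growth variances + 1 covariance = 5, plus 1 common residual variance or T free ones.

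| T | Moments | Parameters, common / free residuals | Degrees of freedom |
|---|---|---|---|
| 2 | 2 + 3 = 5 | 6 / 7 | -1 / -2 |
| 3 | 3 + 6 = 9 | 6 / 8 | +3 / +1 |
| 5 | 5 + 15 = 20 | 6 / 10 | +14 / +10 |

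A numerical rank check agrees. At two occasions the rank is 5, below the 6 or 7 parameters; at three and at five occasions it is full. So two occasions do not identify this model without added constraints, such as fixing a variance. The difference between arms in mean change is still estimable. The count is for a continuous outcome and does not carry over directly to a negative binomial model.

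**The case against.** **The subscale sentence does not exclude later use.** It says when the scale is given, not that it is given at no other time. Section 10 lists conduct disorder among the primary youth constructs, says assessments are repeated, and points to a timeline table that is not legible in the text available to us. This stands in part. A reader might infer that no conduct ratings will be collected after treatment; the documents do not support that. The contradiction remains, because the general wording gives this scale no third occasion. Where the protocol wants a measure at every visit it can say so, as it does for urine samples.

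**The SAP does not assign the growth model to this scale.** This stands. A reader might infer that the SAP's own condition fails for a primary outcome. But the SAP's remark is about the data in general, and its four main adolescent outcomes do not name conduct disorder. The only link is the SAP's mention of problem behaviours as an example of a count outcome. The protocol describes the subscale in similar terms ("Youth problem behaviors will be measured using the Conduct Disorder instrument"), but nothing says that the count is this scale.

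**Methods for two occasions are already listed.** Protocol section 12 names analysis of variance and regression among others. The SAP plans effect sizes at single times and, in its mediation models, an index of change from baseline. So it would be wrong to infer that a treatment effect on this scale cannot be estimated. None of these methods is assigned to this scale, however.

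**Conduct is measured elsewhere.** Section 10 says: "Parents will complete the Child Behavior Checklist". A parallel youth form has a conduct scale too, and the re-offending risk inventory has a conduct domain. This limits the harm. None of them has stated follow-up occasions of its own, and none is named as the measure of the primary outcome; but the endpoint section does not name the subscale either.

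**Conclusion.** The concern holds as an internal contradiction that should be reconciled. As written, the caregiver subscale has two occasions and covers none of the three planned follow-up points on the likelier reading of termination, or one of three on the other. If that sentence governs, the scale gives no 3- or 6-month effect. On the likelier reading it also gives no evidence of durability, and its scores span roughly 24% to 31% of the CIFFTA arm's observation period. A linear growth model with random intercept and slope could not be fitted to it without added constraints; whether the SAP intends that model here is not stated.

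The conclusion rests on taking the instrument-specific sentence at face value. If the timeline table shows the subscale at the follow-up interviews, only the wording needs correction. The SAP describes its analyses as preliminary, and a comparison of arms adjusted for intake remains available. The point is worth fixing but does not undermine the trial. Confidence is medium.

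**What to change.** 1. Amend the Conduct Disorder paragraph in section 10 so that the subscale is given at intake, outtake and the 3-, 6- and 12-month interviews in both arms.
2. Reconcile sections 3 and 8, and the Study Process, Conduct Disorder and Overview paragraphs of section 10, with the timeline table. Section 8 needs particular care: it shows only a booster session at 3 months and no 6-month assessment.
3. Put outtake and all follow-ups on one clock in both arms, for example fixed times from randomisation, whether or not the family is still in treatment. If so, the Overview paragraph, which counts from the end of the intervention, must change too.
4. State in the SAP which model is used for this scale.

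Cost: five occasions less the present two is three added ratings, so 3 x 22 = 66 items per family and 3 x 88 = 264 administrations before attrition. If termination already means 12 months, 2 x 22 = 44 of those items fall at the 3- and 6-month interviews and the other 22 at outtake. Caregiver interviews become slightly longer.

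Fallback: if the scale stays at two occasions, define termination as outtake. State in the SAP that the scale is outside the growth models, compare the outtake score between arms adjusted for the intake score, and make no durability claim from it. This costs a few sentences and no data collection.
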